2. To assess the effects of the NMDA antagonist, memantine, on PPI and neurocognition in healthy subjects, and the moderating roles of personality and genotype in these effects. 30 healthy subjects will complete a within-subject study of placebo vs. 20 mg memantine (p.o.) on two separate days, completing measures of sensorimotor gating and neurocognition on each test day. All subjects will be characterized in terms of specific genetic and personality characteristics.

3. To assess the effects of the NMDA antagonist, memantine, on PPI and neurocognition in schizophrenia patients, and the moderating roles of genotype in these effects. 60 well-characterized and clinically stable individuals with schizophrenia will complete a within-subject study of placebo vs. 10 mg memantine (p.o.) (n=30) or placebo vs. 20 mg memantine (n=30) on two separate days, completing measures of sensorimotor gating and neurocognition on each test day. All subjects will be characterized in terms of specific genetic characteristics.

Figure 1. Schematic "flow chart" of current studies

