Effects of memantine (MEM) vs. placebo (PBO) on WM (%ile score from MCCB, see text). WM was increased by MEM in 7 out of 8 subjects, and unchanged in the 8th. In these subjects ($F=10.68$, $p<0.015$), MEM also significantly increased PPI. This ongoing study is conducted with a double-blind, balanced order design.

The implications of these preliminary findings are potentially quite significant, as they suggest that MEM might enhance PPI and WM, particularly among subgroups of individuals carrying "biomarkers" that include low baseline PPI, high novelty seeking, and/or the Val/Val COMT genotype. If this same pattern of results is detected in clinical populations, it will suggest a means to prospectively identify patients in whom memantine (or other putative pro-cognitive agents) can enhance specific neurocognitive abilities (e.g. WM) to synergize with therapeutic interventions (e.g. cognitive training) that rely on these abilities. We are currently planning to test this prediction in clinical populations, including patients with schizophrenia, who are enrolled in IRB-approved clinical trials of cognitive training.

Summary of Progress to Date

A. Drug Effects on Prepulse Inhibition of Startle:

1. We carefully examined the effects of 4 dopamine agonists (amphetamine, 20 mg), bromocriptine, 1.25 mg), pramipexole (0.125 and 0.175 mg) and amantadine, 200 mg) and one NMDA antagonist (memantine, 20 and 30 mg) on prepulse inhibition (PPI) and related measures, and reported on these effects in five papers (below). Paradigms were modified to increase the sensitivity to drug effects (e.g. via use of within-subject designs or optimal stimulus parameters), and new paradigms were developed to provide new insights into these drug effects (e.g. via the development of a novel sensory gating paradigm). Our findings identified quite distinct effects of these drugs in our behavioral paradigms; for example, amphetamine on the one hand, and amantadine and memantine on the other, produced opposite effects on PPI, with amphetamine significantly disrupting and amantadine and memantine significantly increasing PPI. These effects were not predicted based on our preclinical findings in rats, and have led to new hypotheses and insights related to cross-species differences in the regulation of sensorimotor gating.

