For example, to assess the effects of memantine on "gating" measures in schizophrenia patients, the primary measure will be evaluated by 2-way repeated-measure ANOVA of PPI with memantine dose and prepulse interval as within-subject factors. The hypothesis that memantine will increase PPI in schizophrenia patients will be confirmed by a significant effect of dose (active > PBO) or significant dose x interval (int) interaction and post-hoc comparisons at one or more prepulse intervals. Existing data (see above) provide a strong *a priori* prediction that the 120 ms prepulse interval will be most sensitive to PPI-enhancing effects of MEM. The effect size (d) for PPI-enhancement by 20 mg memantine in HCS was 0.91; with a similar "d" in patients, 30 patients/dose yields power of 0.92 to detect the predicted memantine effects; with maximum expected attrition (n=24), power is 0.85. Past findings also lead to the prediction that these MEM effects would be most robust in subjects exhibiting the lowest basal PPI levels (d=1.80). Using a median split of mean basal (screening) PPI levels, ANOVA as above will detect a significant interaction of memantine dose x basal PPI level, or dose x basal level x int, and significant post-hoc comparisons at one or more prepulse intervals (again, 120 ms being the strongest *a priori* candidate). Given the published "d" in control subjects, a comparable "d" in the proposed 12-15 "low PPI" patients/dose group would yield power >0.95 to detect the predicted memantine effects.

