Lastly, based on the impact of basal PPI level and personality measures in controls, we hypothesize that a critical moderating factor underlying PPI memantine sensitivity is COMT Val158Met genotype; specifically, we predict that “Val/Val” individuals will be most sensitive to memantine-enhanced PPI. This will be tested in two ways: first, by ANOVA as above, with COMT status as a between-subject factor, and memantine dose and prepulse interval as within-subject factors. Significant genotype x dose or genotype x dose x int interactions, with appropriate post-hoc comparisons, would confirm the hypothesis. Estimating $d=1.53$, based on the mean “d” of two “COMT phenotypes” in controls – low basal PPI ($d=1.80$) and high “novelty seeking” personality ($d=1.27$) - the proposed 11 Val/Val and 7 Met/Met patients/dose group would yield power of 0.90 to detect genotype-sensitive memantine effects. It is possible that various factors (including a skewed distribution of allele frequencies, or substantial genotype effects on basal PPI levels) might preclude detection of a significant 2- or 3-way interaction. A secondary (albeit weaker) test of the hypothesis will utilize separate ANOVAs in Val/Val vs. Met/Met subgroups, with predicted PPI-enhancing effects of memantine in the Val/Val but not Met/Met subgroups. Previous reports also predict a significant main effect of genotype, with PPI levels following the Met/Met>Val/Met>Val/Val gradient. Logistic regressions might be used, with genotype coded to reflect “dose” of the Met allele (Val/Val=0, Val/Met=1, and Met/Met=2), to assess the distribution of the neurophysiological and neurocognitive measures. All analyses will be conducted independently for each dose group. If comparable effects are evident with 10 and 20 mg doses, dose groups may be pooled to increase power for exploratory analyses (e.g. to detect genotype x drug effects).

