Statistical Analysis Plan

Biomarker Strategies for Medication-Enhanced Cognitive Training in Schizophrenia

NCT01555697

NIMH-R34-MH093453-NS

Latest IRB approval date: August 17, 2019

IRB expiration date: August 15, 2020

The primary statistical considerations for these data are those required to test the primary hypothesis that memantine (MEM) would enhance sensorimotor gating and neurocognition in schizophrenia (SZ) patients. The operational measure of sensorimotor gating was prepulse inhibition of startle (PPI). The primary hypothesis was tested by a 2-way repeated-measure ANOVA of PPI with MEM dose and prepulse interval (10, 20, 30, 60 or 120 ms) as within-subject factors. The key dependent measure was %PPI, calculated according to common practices in the literature. The hypothesis that MEM will increase PPI in SZ patients was to be confirmed by a significant main effect of drug (active > PBO) or significant interaction among the variables of drug, dose (10 or 20 mg), diagnosis (healthy subject (HS) or SZ) or prepulse interval, and informative post-hoc comparisons. The assumptions behind these analyses range from the standard assumptions underlying the use of parametric analyses, to those specific to prepulse inhibition, e.g. related to the potential confounding effects of drug or diagnosis effects on startle magnitude. Data were demonstrated to be normally distributed and drug effects on PPI were shown to be independent of changes in startle magnitude. Analyses confirmed the hypothesis for the 20 mg dose of MEM in SZ patients.

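### Supporting analysis: test basal-PPI moderation of the memantine effect on continuous screening PPI rather than a median split, and say what the >0.95 power refers to

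*Protocol*

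**What the plan says.** Protocol section 9, part j (Statistics) expects memantine effects to be "most robust in subjects exhibiting the lowest basal PPI levels", with d=1.80 taken from healthy controls. The planned test is: "Using a median split of mean basal (screening) PPI levels, ANOVA as above will detect a significant interaction" of memantine dose with basal PPI level, or of dose, basal level and prepulse interval, followed by post-hoc comparisons. The only power given beside this test is for the 12-15 low-PPI patients in each dose group: "patients/dose group would yield power >0.95 to detect the predicted memantine effects". The overall drug effect has its own figures: "30 patients/dose yields power of 0.92 to detect the predicted memantine effects" at d=0.91, falling to 0.85 with 24 patients.

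The same part j adds "All analyses will be conducted independently for each dose group". Since 12-15 is half of 24-30, I infer that the split is made within each dose group.

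The SAP confirms the PPI hypothesis through a main effect of drug or an "interaction among the variables of drug, dose (10 or 20 mg), diagnosis (healthy subject (HS) or SZ) or prepulse interval". Its cognitive analysis adds test domain. Basal PPI appears in neither list, so section 9 is the only plan for this question.

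Aim 3 in Protocol section 6 names another moderator: "and the moderating roles of genotype in these effects". Section 8 counts low baseline PPI among the biomarkers of interest, and says that if the pattern also holds in patients, "it will suggest a means to prospectively identify patients in whom memantine" can help.

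**The concern.** The prediction is graded: the lower the basal PPI, the larger the effect. A median split treats a patient just below the median like the lowest in the group, and separates two patients who lie on either side of it. When the true relation is graded, that costs power, and a dose group has only 24-30 patients. The cut-off also depends on who was enrolled, so it is an unstable basis for a biomarker.

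A second, smaller issue is that the power figure beside the interaction test describes the drug effect inside one half. A reader could take it as the power of the interaction.

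What is at stake is a supporting result on who responds. The test of whether memantine changes PPI does not depend on it.

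**Working it through.** **1. The plan's own figures.** Inputs from Protocol section 9, part j: d=0.91 overall with n=30 or 24; d=1.80 in 12-15 low-PPI patients; alpha 0.05, taken as two-sided. A paired t-test with d/√2 (raw-score d, zero between-day correlation) gives:
- overall: 0.93 at n=30 (stated 0.92) and 0.86 at n=24 (stated 0.85);
- low-PPI patients: 0.98 at n=12 and above 0.99 at n=15 (stated >0.95).

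A two-sample t-test with the stated n per group gives 0.93, 0.87, 0.99 and above 0.99. Either way, >0.95 is correct for the drug effect in the low-PPI subgroup.

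**2. Information lost by the split.** With two test days, the drug by basal-PPI interaction is the regression of each patient's change (memantine minus placebo) on screening PPI, x. For normal x and a linear relation, splitting at the median multiplies the correlation by √(2/π)=0.80. It therefore keeps 2/π=0.64 of the information and loses 1-0.64=0.36. Thirty patients then count as about 30×0.64=19.

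**3. Power under linear moderation.** Simulation: 40,000 data sets per cell, x normal, change = -ρx + √(1-ρ²)·e, two-sided 0.05. The documents do not give ρ, so a range is shown. All three tests reject about 5% of the time under the null.

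| n | ρ | Split | Continuous | Ranks of x |
|---|---|---|---|---|
| 24 | 0.4 | 0.33 | 0.50 | 0.48 |
| 24 | 0.5 | 0.51 | 0.73 | 0.70 |
| 24 | 0.6 | 0.70 | 0.90 | 0.88 |
| 30 | 0.4 | 0.41 | 0.61 | 0.58 |
| 30 | 0.5 | 0.61 | 0.83 | 0.80 |
| 30 | 0.6 | 0.80 | 0.96 | 0.94 |

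Over ρ from 0.2 to 0.8 the gain from the continuous test is about 1 to 22 points. At ρ=0.8 it has nearly gone (0.97 against 1.00 at n=24).

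**4. When the split does better.** Let the effect be a step at the population median, with half-differences of 0.6-1.78 SD of change. The split then beats a raw slope by about 2-8 points for normal x and about 6-24 points for strongly skewed x (lognormal, sigma 0.8). Against ranks it differs by no more than about 3 points either way. If the step is forced to fall exactly at each sample's own median, the split's most favourable case, its lead for normal x is about 7-25 points over the raw slope and 3-16 over ranks.

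**5. Linear in a strongly skewed x.** For ρ=0.4 to 0.6 at n=24, power is 0.21-0.43 (split), 0.44-0.78 (raw slope) and 0.32-0.66 (ranks). Ranks lose about 10-14 points to the raw slope and still beat the split.

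**6. Power of the planned split interaction.** The documents give no high-half effect. Suppose d=1.80 describes the lower half of the sample that gave 0.91 (not stated), and call the high-half d m.
- d in SDs of change: solve ((1.80+m)/2)/√(1+(1.80-m)²/4)=0.91. Then m=0.41, the difference is 1.39, and power is 0.90 (12 per half) and 0.96 (15 per half).
- d in raw-score SDs, zero between-day correlation: replace the 4 under the root by 8. Then m=0.27 and the difference is 1.53, or 1.53/√2=1.08 in SDs of change. Power is 0.72 and 0.82.

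**The case against.** The benefit is conditional. Linearity, the distribution of screening PPI and the strength of moderation are all assumed, and step 4 shows that the split can win. It also mirrors the low-PPI contrast from which the prediction was drawn. This stands: it is why ranks and a plot belong in the remedy and why the halves should still be shown.

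The simulation compares one change score per patient, whereas the plan also accepts a three-way interaction with prepulse interval. That is fair. The figures compare the two codings of basal PPI; they are not the power of the full planned rule.

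The >0.95 sentence directly follows the interaction sentence. For genotype, the plan averages subgroup effect sizes (1.80 and 1.27) and uses the result to power detection of genotype-sensitive effects. Read that way, d=1.80 for 12 against 12 gives 0.99, so the figure could be meant for the interaction. But its wording counts only low-PPI patients. A difference of 1.80 also needs no effect in the high half, and then the overall d would be 0.90/√(1+1.80²/4)=0.67 on the change-score scale, not 0.91, if both values come from one sample. The text needs clarifying; it is not wrong.

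Three stronger inferences are tempting and unsupported:
- **The planned interaction is underpowered.** Step 6 gives about 0.90-0.96, or 0.72-0.82 at zero between-day correlation. Zero correlation also sits badly with basal PPI being a stable moderator.
- **A median-based label is useless for a new patient.** The median is a value on the PPI scale and can be applied; it is only sample-dependent and unstable. Section 9, part e also describes high and low PPI by quartiles of a normal population.
- **The main conclusion is compromised.** The primary analysis does not use basal PPI.

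**Conclusion.** The point holds as an inexpensive improvement to a supporting analysis. Basal-PPI moderation is tested only through a median split of a continuous measure already in hand. If moderation is roughly linear and screening PPI roughly normal, the continuous test gains about 15-22 points of power at correlations of 0.4-0.6, and little when moderation is very strong. If the effect is a step near the median the advantage reverses, by a few points for normal screening PPI and by more if it is strongly skewed. The documents do not show which case applies; the graded wording of the prediction favours the continuous test. On power, the finding is limited to a request for clarification. The genotype moderator of Aim 3 and the primary drug test are unaffected.

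**What to change.** In Protocol section 9, part j, and in the SAP if this question is to be reported:
- In each dose group, make drug by centred continuous screening PPI the moderation test in the repeated-measures model, keeping the term with prepulse interval.
- Enter screening PPI as ranks or transformed if it is skewed, with that choice made from the screening data alone.
- Plot drug effect against screening PPI to check shape and influential points, and report the slope on the PPI scale. Keep the median halves as a descriptive display.
- State that >0.95 is the power for the drug effect in 12-15 low-PPI patients. If a power for the interaction is wanted, give it separately with its assumed high-half effect and between-day correlation.

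The cost is a few lines of text and no new data. The SAP reports that drug effects have already been examined, so a run on the data in hand must be labelled post hoc. The statistical price is some power if the effect really is a step, and sensitivity of a raw slope to extreme values at n=24-30. Ranks reduce both, at about 0-3 points when moderation is linear and screening PPI normal, but about 10-14 points against the raw slope when moderation is linear in a strongly skewed PPI.

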Main effects of memantine on WM will be tested by one-way ANOVA with memantine dose as a within-factor. Based on $d=0.73$ for increased WM after 20 mg MEM in controls (see above), the proposed 30 patients/dose group would yield power of 0.79 to detect significant WM-enhancing effects. While preliminary data yield less robust predictions for COMT subgroup sensitivities in memantine effects on WM performance, given the significant correlation of WM and PPI, and known impact of COMT genotype on PPI levels, we predict some differential (Val/Val > Met/Met) memantine sensitivity in this measure. If we estimate effects of COMT status on WM memantine-sensitivity to be comparable to those for PPI (65% increase in effect size), then the estimated d for Val/Val vs. Met/Met sensitivity should be 1.20, and the proposed genotype subgroup sizes would yield power of 0.65 to detect genotype-sensitive memantine effects on WM.

Secondary “biomarkers” are MMN and GBS. For MMN, positive memantine effects will be detected by increased MMN amplitude at electrode Fz. For GBS, positive memantine effects would be detected by increased 40 Hz evoked power at electrode Fz. Unlike those for PPI, predictions of positive memantine effects on MMN and GBS are not based directly on previous findings from our laboratory, using measures identical to those proposed herein. However, based on reports in healthy subjects from other laboratories of memantine effects on MMN ($d=0.87$) and ketamine effects on GBS ($d=0.69$), the proposed 30 patients/dose group would yield power of 0.90 and 0.75, respectively, to detect positive memantine effects on these measures.

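### The 0.90 power quoted for the COMT by memantine test is for an 11 v 7 comparison, where it is nearer 0.84, and does not describe an interaction test whose number of genotype levels is unstated

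*Protocol*

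**What the plan says.** Protocol section 9.j (Statistics, power considerations) treats COMT Val158Met genotype as the key moderator of the PPI response to memantine and expects Val/Val patients to respond most. The first test is described as "first, by ANOVA as above, with COMT status as a between-subject factor, and memantine dose and prepulse interval as within-subject factors". A genotype by dose interaction, or a three-way interaction that adds prepulse interval, counts as confirmation when suitable post-hoc comparisons support it.

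The power statement is that "the proposed 11 Val/Val and 7 Met/Met patients/dose group would yield power of 0.90 to detect genotype-sensitive memantine effects", at an assumed d of 1.53 (the average of 1.80 and 1.27 from two control-subject subgroups). For working memory (WM) the section says "we predict some differential (Val/Val > Met/Met) memantine sensitivity in this measure", takes d as 1.20 and quotes power of 0.65.

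The section also says: "Previous reports also predict a significant main effect of genotype, with PPI levels following the Met/Met>Val/Met>Val/Val gradient". It mentions coding genotype by number of Met alleles (0, 1, 2), but only for a logistic regression that might be used. A second, admittedly weaker test runs separate ANOVAs in the two homozygote groups. The two dose groups are analysed separately, so each analysis has 30 patients. The SAP does not mention COMT.

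**The concern.** The test that decides the hypothesis and the test whose power is quoted are not shown to be the same. The 11 and 7 patients in the power statement make a two-group comparison on 1 df. The analysis is an ANOVA "with COMT status as a between-subject factor", and the surrounding text names three genotypes. If all three are levels of the factor, the genotype by dose interaction has 2 df, and its power depends on how Val/Met patients respond to the drug, which the plan does not predict. If only the homozygotes enter, the test matches the power statement, but 30 − 11 − 7 = 12 patients (40%) drop out of the moderator analysis without this being said.

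The 0.90 also looks high for the comparison it describes. A reader would take it as the chance of detecting the plan's main moderator effect, and would read a null interaction as stronger evidence against moderation than it is.

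**Working it through.** **Inputs.** From protocol section 9.j: alpha 0.05; d = 1.53 (PPI) and 1.20 (WM); 11 Val/Val and 7 Met/Met per dose group; 30 patients per dose group. Assumed: two-sided testing (sidedness is not stated, but an ANOVA F test has no direction); 12 Val/Met patients, from 30 − 11 − 7; d is the Val/Val minus Met/Met difference in drug response, in SDs of the drug–placebo difference; the prepulse-interval factor is ignored.

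**1. The quoted comparison, 11 v 7.** The noncentrality is d / √(1/11 + 1/7) = d × √(77/18), with 16 df and critical t = 2.120.

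- PPI: 1.53 × 2.068 = 3.164, power 0.844. The protocol says 0.90.
- WM: 1.20 × 2.068 = 2.482, power 0.645. The protocol says 0.65.

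So the two-sided exact t test reproduces the WM figure but not the PPI figure. In its two-sample form with 30 per group it also returns the protocol's main-effect figures of 0.79 (d = 0.73: 0.794) and 0.75 (d = 0.69: 0.748). Other methods come closer to 0.90 for PPI: 0.886 by the two-sided normal approximation and 0.916 by a one-sided t test. For WM these give 0.699 and 0.767, not 0.65. None of these methods produces both COMT figures.

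**2. Three-level interaction, 2 df.** With mean drug responses μ for the 11/12/7 patients and unit SD, λ = Σ n(μ − μ̄)², referred to noncentral F(2, 27) with critical value 3.354. For PPI with Val/Met midway, the means are 1.53, 0.765 and 0:

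- μ̄ = (11 × 1.53 + 12 × 0.765) / 30 = 0.867
- λ = 11 × 0.663² + 12 × 0.102² + 7 × 0.867² = 4.835 + 0.125 + 5.262 = 10.22
- power 0.777

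**3. Val/Val minus Met/Met contrast, error pooled over all 30.** The noncentrality is as in step 1, now with 27 df and critical t = 2.052. Power is 0.862 (PPI) and 0.667 (WM). The Val/Met mean does not enter.

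**4. Varying the Val/Met response** (0 = like Met/Met, 1 = like Val/Val):

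| Val/Met position | PPI, 2-df | PPI, contrast | WM, 2-df | WM, contrast |
|---|---|---|---|---|
| 0 | 0.937 | 0.862 | 0.769 | 0.667 |
| 0.25 | 0.849 | 0.862 | 0.636 | 0.667 |
| 0.5 | 0.777 | 0.862 | 0.555 | 0.667 |
| 0.75 | 0.782 | 0.862 | 0.560 | 0.667 |
| 1 | 0.860 | 0.862 | 0.649 | 0.667 |

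The lowest 2-df values, near position 0.6, are 0.768 for PPI and 0.546 for WM.

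**5. Attrition.** The protocol allows for 24 patients per dose group but gives no genotype split. Assuming 9/9/6 or 9/10/5, PPI power for the contrast is 0.790 or 0.744, and for the 2-df test with Val/Met midway 0.682 or 0.639.

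**The case against.** The best defence is that COMT status may mean Val/Val against Met/Met only. The power statement and the second test both use just those groups. The planned test then has 1 df and is the one whose power is quoted, and pooling error over all 30 adds only about 2 points (0.844 to 0.862 for PPI). This stands as a possible reading. It leaves the 0.90 too high and the exclusion of 12 patients unstated.

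The protocol also warns that the interaction may not be detected and provides the subgroup ANOVAs as a fallback. It allows confirmation through the three-way interaction too, which the calculation above does not cover. So 0.78 is the power of the genotype by dose interaction alone, not the overall chance of confirmation.

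A reader might infer something stronger: that the plan predicts an ordered genotype effect, so ignoring the order costs 9 to 12 points against a linear allele-dose contrast. With Val/Met midway the figures do run that way (PPI 0.869 v 0.777, WM 0.676 v 0.555). But the stated gradient concerns PPI levels, as a main effect of genotype. For drug response the plan says only that Val/Val is most sensitive and exceeds Met/Met. The midpoint is therefore an outside assumption, and the sign of the gain depends on it. For PPI the linear contrast has less power than the 2-df test if Val/Met responds like Met/Met (0.920 v 0.937) or like Val/Val (0.799 v 0.860). Choosing between those two tests is a trade-off, not an error in the plan.

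**Conclusion.** The point holds as a mismatch between the quoted power and the test described. For the 11 v 7 comparison, 0.90 should be about 0.84, some 6 points lower, under two-sided testing at 0.05. For a three-level interaction the shortfall from 0.90 is about 12 points with Val/Met midway; power there can lie anywhere from about 0.77 to 0.94 for PPI and 0.55 to 0.77 for WM, because the plan does not fix the Val/Met response. The WM figure of 0.65 is right for 11 v 7 but not for a three-level test with Val/Met midway.

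These figures take the protocol's d values at face value as between-genotype differences and use the inferred 12 Val/Met patients. The documents do not establish that the factor has three levels. Nor do they support a fixed power loss from ignoring genotype order.

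**What to change.** In protocol section 9.j, and in the SAP if the COMT analysis is to be reported:

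- State the number of COMT levels.
- Keep all three genotypes in the model. Name the 1-df Val/Val minus Met/Met contrast of the drug–placebo difference, with error pooled over all 30 patients in the dose group, as the confirming test. It is the comparison the hypothesis describes, and its power (0.86 PPI, 0.67 WM) does not depend on where Val/Met falls.
- Say whether the PPI contrast is averaged over prepulse intervals or taken at one named interval, and what role the three-way interaction keeps.
- Report the 2-df interaction and an allele-dose (0/1/2) trend in drug response as supporting analyses.
- Replace 0.90 with the power of the test chosen, giving the method, the sidedness and a figure at 24 patients.

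This needs no new data, only wording and one contrast statement. The statistical cost is lower power than the 2-df test if Val/Met patients respond like Met/Met patients: 0.86 v 0.94 for PPI and 0.67 v 0.77 for WM. Because the SAP already reports results for the primary hypotheses, a contrast named after the genotype-by-drug data have been examined must be labelled post hoc.

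### Protocol 9.j: the two genotype power figures, 0.90 for PPI and 0.65 for working memory, cannot both come from one stated method in the same 11 and 7 patients

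*Protocol*

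**What the plan says.** Aim 3 (Protocol Section 6) covers memantine effects "on PPI and neurocognition in schizophrenia patients, and the moderating roles of genotype in these effects". Section 9.j tests the genotype hypothesis for PPI in two ways. The first is an ANOVA with COMT genotype between subjects and memantine dose and prepulse interval within subjects: "Significant genotype x dose or genotype x dose x int interactions, with appropriate post-hoc comparisons, would confirm the hypothesis". The second, which the plan calls weaker, runs separate ANOVAs in the Val/Val and Met/Met subgroups.

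For PPI, d is set at 1.53, the mean of two effect sizes seen in healthy phenotype groups (1.80 and 1.27), and "the proposed 11 Val/Val and 7 Met/Met patients/dose group would yield power of 0.90 to detect genotype-sensitive memantine effects".

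For WM, genotype effects are taken as "comparable to those for PPI (65% increase in effect size), then the estimated d for Val/Val vs. Met/Met sensitivity should be 1.20". The power claim attached to this d refers back to the PPI cells without repeating their numbers: "the proposed genotype subgroup sizes would yield power of 0.65 to detect genotype-sensitive memantine effects on WM".

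The main-effect figures come from the same section. For PPI at d=0.91, "30 patients/dose yields power of 0.92 to detect the predicted memantine effects; with maximum expected attrition (n=24), power is 0.85". For WM, "Main effects of memantine on WM will be tested by one-way ANOVA with memantine dose as a within-factor", with d=0.73 and a stated power of 0.79.

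Alpha is 0.05. Section 9.j does not give the sidedness, the SD in which d is expressed, or a correlation between the two test days.

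**The concern.** The two genotype statements share their cells, alpha and stated purpose. They differ only in outcome and in d, so one method should carry the reader from one figure to the other. It does not: the rise from 0.65 to 0.90 is larger than the rise in d allows.

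The missing SD basis makes this hard to resolve. The study is a crossover, and the power of a within-subject contrast depends on whether d is scaled to a single day's SD or to the SD of the drug-placebo change.

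What is at stake is how a null genotype result would be read. At power 0.90 the miss rate is 10%. On the convention that fits the WM figure, it is 16%.

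**Working it through.** **Inputs (Protocol 9.j).** Cells are 11 Val/Val and 7 Met/Met per dose group. PPI: d=1.53 (mean of 1.80 and 1.27 = 1.535), stated power 0.90. WM: d=1.20 (0.73 x 1.65 = 1.2045), stated power 0.65. Alpha is 0.05. The between-day correlation r is not in the documents, so any value below is an assumption.

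**Step 1: reproduce the stated figures.** For two genotypes and two treatment days, the genotype x drug test is a two-sample t test on the drug-placebo change. With d on the SD of that change, the noncentrality is d x sqrt(11 x 7/18) = 2.068d, with df 16 and a two-sided critical value of 2.120.

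- WM: 2.068 x 1.20 = 2.482, power 0.645 (0.648 with d=1.2045). This matches the stated 0.65.
- PPI: 2.068 x 1.53 = 3.164, power 0.844 (0.846 with d=1.535). This does not match 0.90.

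A simulation of 200,000 trials gives 0.644 and 0.843.

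**Step 2: try other conventions.**

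| Convention | PPI (stated 0.90) | WM (stated 0.65) |
|---|---|---|
| Two-sided t, 11 v 7 | 0.844 | 0.645 |
| Two-sided normal approximation | 0.886 | 0.699 |
| One-sided t | 0.916 | 0.767 |
| Two-sided t, error df 27 (three genotypes) | 0.862 | 0.667 |
| Two-sided t, 9 v 9 | 0.861 | 0.667 |
| Val/Val alone, paired, r=0, n=11: noncentrality d/sqrt(2) x sqrt(11), df 10 | 0.898 | 0.718 |

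Each row misses at least one figure.

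**Step 3: a check that does not use the scale of d.** If both outcomes share the same SD basis, r and cells, these cancel. At df 16, power 0.90 needs noncentrality 3.455 and power 0.65 needs 2.497, a ratio of 1.384 (1.364 to 1.404 allowing for rounded powers). The stated ratio is 1.53/1.20 = 1.275, and at most 1.535/1.195 = 1.285 with rounding.

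**Step 4: what the SD basis does.** If d is on the single-day SD, the genotype noncentrality becomes 2.068d/sqrt(2(1-r)), and the main-effect noncentrality is d x sqrt(30)/sqrt(2(1-r)) with df 29.

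| Assumed r | Genotype PPI | Genotype WM | Main effect PPI | Main effect WM |
|---|---|---|---|---|
| 0 | 0.56 | 0.38 | 0.93 | 0.78 |
| 0.25 | 0.68 | 0.48 | 0.98 | 0.88 |
| 0.5 (same as change-score SD) | 0.84 | 0.645 | 0.998 | 0.97 |
| 0.7 | 0.97 | 0.85 | >0.999 | 0.999 |

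Solving for r, 0.90 needs r=0.58 for PPI and 0.65 needs r=0.51 for WM. Separate correlations could therefore give both figures. If the main-effect d values are on the same scale, those r values put the main effects at >0.999 and 0.97, not the stated 0.92 and 0.79.

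**Step 5: which method lies behind the other figures?** Two candidates fit almost equally well.

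| Stated | Independent groups, n per arm | Paired, r=0 |
|---|---|---|
| PPI n=30: 0.92 | 0.934 | 0.926 |
| PPI n=24: 0.85 | 0.870 | 0.855 |
| WM: 0.79 | 0.794 | 0.780 |
| MMN: 0.90 | 0.912 | 0.903 |
| GBS: 0.75 | 0.748 | 0.733 |

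The largest error is 0.020 for the first and 0.017 for the second. The stated figures do not identify the method.

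**The case against.** The best defence is that 0.90 belongs to a different test. The PPI d of 1.53 averages effects seen within sensitive phenotype groups, and Section 9.j does plan a Val/Val-only ANOVA. A paired test at r=0 in 11 patients gives 0.898, and the same formula fits the main effects well. On that reading 0.65 is the odd figure (0.718 by that formula), and the defect is an unlabelled test. This stands as a possibility. It does not remove the problem: the 0.90 sentence directly follows the interaction criterion and cites both genotype cells, and the weaker subgroup test is introduced only afterwards.

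It can also be said that PPI and WM need not share a correlation. That is true, and Step 3 holds only if they do. But no correlation is given for either.

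Finally, the consequence is small. The plan itself warns that allele frequencies or genotype effects on basal PPI may prevent a significant interaction, and it allows the doses to be pooled for exploratory genotype analyses. The SAP names no genotype test. All of this stands and limits the weight of the point.

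**Conclusion.** The two genotype powers cannot be reconciled from what the plan states. The result rests on the cells being the same 11 and 7, alpha 0.05, and one convention for both outcomes.

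Three stronger readings are tempting, and the documents support none of them.

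- **That 0.90 is simply wrong and should read 0.84.** This holds only for the interaction with d on the change-score SD (or r=0.5). The Val/Val-only reading gives 0.90.
- **That genotype power is really about 0.56.** This needs the single-day SD and r=0. The 65% scaling from the WM main-effect d to 1.20 hints at one common scale, but the plan does not say which, and nothing in it supports zero correlation.
- **That r can be recovered from the pilot result in Section 8**, "In these subjects ($F=10.68$, $p<0.015$), MEM also significantly increased PPI". The wording leaves open whether F refers to WM or PPI, the sample is 8 subjects, and the PPI d of 0.91 is not tied to those subjects.

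The impact is minor. On the change-score basis the interaction power for PPI is still above 0.80, the stated main-effect powers are not too high by more than about 0.01 at any r of zero or above, and 30 patients per dose is not put in doubt.

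**What to change.** Before the first power figure in Section 9.j, state once: the SD basis of d; if it is the single-day SD, the between-day correlation for PPI and for WM, ideally from the laboratory's own memantine crossover data; and two-sided 0.05. Then recompute the main effects as a one-sample t test on the drug-placebo change, and both genotype figures as a two-sample t test on that change (11 v 7, df 16).

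- If d is on the change-score SD, the text would read: genotype x drug power 0.84 (PPI, d=1.53) and 0.65 (WM, d=1.20); main effects 0.998 (PPI) and 0.97 (WM) at n=30.
- If d is on the single-day SD, give the values at the stated r for each outcome.
- If 0.90 was meant for the Val/Val-only ANOVA, label it so and give the interaction power separately.

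The cost is text only, with no added patients and no change of analysis. The stated PPI genotype power may fall. It would rise above 0.90 only if d is on the single-day SD and r exceeds about 0.58.
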